## 8.6.2 Summaries of Baseline Characteristics, Demographics, and Other Analyses

The number and percentage of subjects screened, the primary reasons for screening failure, and the primary reason for discontinuation will be displayed. Demographic variables, baseline characteristics, primary and secondary diagnoses, and prior and concomitant therapies will be summarized either by descriptive statistics or categorical tables.

## 8.7 Interim Analyses

### 8.7.1 Safety Interim Analyses

An ongoing safety review will be conducted for this study and upon request by the Regulatory Agency. The objective of this safety review is to assess the safety data collected over the duration of the study; the results obtained will be submitted to the Regulatory Agency to seek further direction on the continuation of the study. An interim data listing for safety evaluation will be conducted at 1 year from the date at which the first subject is enrolled into the study.

## 8.8 Multiplicity

This study does not involve multiplicity adjustments.

## 8.9 Sample Size and Power Calculations

### 8.9.1 Sample Size and Power for Safety Analyses

Safety is the primary endpoint. No formal sample size calculations are performed for this study since the primary objective is not to test a predefined hypothesis, but to collect and assess adverse events occurring in subjects treated in a routine clinical setting (see Section 4.2.1). If the planned 150 subjects are enrolled, then, if a certain number of subjects

experience a specific adverse event, serious adverse event, Grade 3+ adverse event, adverse event of special interest (AEOSI) etc. a 95% CI for the true adverse event rate would be:

Number of subjects (%) with AEs	95% confidence interval
8/150 ( 5.33%)	( 2.3%, 10.2%)
15/150 (10.00%)	( 5.7%, 16.0%)
23/150 (15.33%)	(10.0%, 22.1%)
30/150 (20.00%)	(13.9%, 27.3%)
38/150 (25.33%)	(18.6%, 33.1%)
45/150 (30.00%)	(22.8%, 38.0%)
53/150 (35.33%)	(27.7%, 43.5%)

## **8.10 Subgroup Analyses**

No subgroup analyses are planned.

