## 1.0 TRIAL SUMMARY

Abbreviated Title	A Prospective, Open-label, Phase 4 Study to Evaluate the Safety of Pembrolizumab (KEYTRUDA®) in Subjects with Unresectable or Metastatic Melanoma or PD-L1 positive Non-small Cell Lung Cancer (NSCLC) in India (Keynote-593)
Sponsor Product Identifiers	MK-3475 Pembrolizumab (Keytruda®)
Trial Phase	4
Clinical Indication	Unresectable or metastatic melanoma, and non-small cell lung cancer (NSCLC) subjects who are either untreated (PD-L1 $\geq 50\%$ ) or have experienced disease progression after a platinum-containing systemic therapy (PD-L1 $\geq 1\%$ )
Trial Type	Interventional
Type of control	No treatment control
Route of administration	Intravenous
Trial Blinding	Unblinded Open-label
Treatment Groups	Pembrolizumab (Keytruda®)
Number of trial subjects	Approximately 150 subjects will be enrolled, with a minimum of 25 unresectable or metastatic melanoma subjects.
Estimated duration of trial	The Sponsor estimates the trial will end approximately 2 years from the time the last subject provides documented informed consent.
Duration of Participation	
Each subject will participate in the trial from the time the subject provides documented informed consent through the final protocol-specified contact.
 
After a screening phase of 30 days, each subject will be assigned to receive trial treatment with pembrolizumab monotherapy until disease progression is confirmed by the site per Response Evaluation Criteria in Solid Tumors (RECIST 1.1), unacceptable adverse event(s), intercurrent illness that prevents further administration of treatment, Investigator's decision to withdraw the subject, non-compliance with trial treatment or procedures requirements or administrative reasons requiring cessation of treatment, or until the subject has received 35 cycles of pembrolizumab (approximately 2 years), whichever occurs first. Each cycle is defined as 21 days.
 
After the end of treatment, each subject will be followed for the occurrence of adverse events and spontaneously reported pregnancy as described under Section 7.2 of the protocol.
 
Subjects who discontinue for reasons such as radiologic or clinical disease progression, safety events, or investigator or subject decision to stop treatment will have an end of treatment (EOT) visit and a 30-day safety follow-up visit per Section 7.1.4.1.

A list of abbreviations used in this document can be found in Section 12.6.

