#### **3.1 Primary Objective(s) & Hypothesis(es)**

(1) Objective: To assess the safety of pembrolizumab in India in subjects with unresectable or metastatic melanoma, and NSCLC subjects who are either untreated (PD-L1  $\geq 50\%$ ) or have experienced disease progression after a platinum-containing systemic therapy (PD-L1  $\geq 1\%$ ).

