## **4.2 Rationale**

### **4.2.1 Rationale for the Trial and Selected Subject Population**

The purpose of this Phase 4 study is to fulfill the Indian regulatory post-approval requirement for an interventional Phase 4 study for pembrolizumab while granting permission to market the product in India. The safety data collected in this study will help to inform the safety profile of pembrolizumab in subjects treated in India with unresectable or metastatic melanoma and NSCLC subjects who are either untreated (PD-L1  $\geq 50\%$ ) or have received a minimum of 2 cycles of a platinum-containing systemic therapy (PD-L1  $\geq 1\%$ ). Due to the low incidence rate of melanoma in India, the number of melanoma subjects is anticipated to be lower than the number of NSCLC subjects.

Pembrolizumab monotherapy is the current standard of care for the treatment of patients with good Eastern Cooperative Oncology Group (ECOG) performance status (ECOG 0 or 1) and previously untreated, advanced, or metastatic NSCLC with a programmed cell death ligand 1 (PD-L1) TPS  $\geq 50\%$  with no EGFR or ALK genomic tumor aberrations. Approximately 30% of patients with newly diagnosed, advanced NSCLC highly express PD-L1 to a TPS  $\geq 50\%$  [59].

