### 8.1 Statistical Analysis Plan Summary

Key elements of the statistical analysis plan are summarized below; the comprehensive plan is provided in Sections 8.2-8.12.

Study Design Overview	A Prospective, Open-label, Phase 4 Study to Evaluate the Safety of Pembrolizumab (Keytruda®) in Subjects with Unresectable or Metastatic Melanoma or PD-L1 positive Non-Small Cell Lung Cancer (NSCLC) in India
Treatment Assignment	All subjects to be assigned to the same dose/schedule of pembrolizumab
Analysis Populations	ASaT
Primary Endpoint(s)	Safety and tolerability of the protocol treatment as characterized by the adverse event experience
Statistical Methods for Key Safety Analyses	Descriptive statistics will be provided for the rate of safety endpoints.
Interim Analyses	An ongoing safety review will be conducted for this study. An interim data listing for safety evaluation will be conducted at 1 year from the date at which the first subject is enrolled into the study.
Multiplicity	Not applicable
Sample Size and Power	The planned sample size is approximately 150 subjects (with a minimum of 25 subjects with unresectable or metastatic melanoma, and ~125 NSCLC subjects who are either untreated (PD-L1 $\geq$ 50%) or have experienced disease progression after a platinum-containing systemic therapy (PD-L1 $\geq$ 1%). No hypothesis testing will be performed. The goal is to characterize the AEs associated with the use of pembrolizumab in the treatment of subjects, as described above, in India.

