## 8.5 Analysis Populations

### 8.5.1 Safety Analysis Populations

The All Subjects as Treated (ASaT) population will be used for the analysis of safety data in this study. The ASaT population consists of all subjects who received at least 1 dose of trial treatment.

At least 1 laboratory or vital sign measurement obtained subsequent to at least 1 dose of trial treatment is required for inclusion in the analysis of each specific parameter. To assess change from baseline, a baseline measurement is also required.

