## 8.6 Statistical Methods

### 8.6.1 Statistical Methods for Safety Analyses

Safety and tolerability will be assessed by clinical review of all relevant parameters including AEs and laboratory parameters.

The proportion of subjects with AEs of elevated laboratory values that are reported as ECIs described in Section 7.2.3.2 during the study therapy period will be provided along with the corresponding 95% CIs, which will be calculated using the Clopper Pearson method.

In addition, the broad AE categories consisting of the percentage of subjects with any AE, a drug-related AE, a serious AE, an AE which is both drug-related and serious, and those who discontinued due to an AE will be summarized in the same manner [Table 8](#).

Table 8 Analysis Strategy for Safety Parameters

Safety Endpoint	Within Group 95% CI	Descriptive Statistics
Any AE	X	X
Any Serious AE	X	X
Any Drug-Related AE	X	X
Any Serious and Drug-Related AE	X	X
Discontinuation due to AE	X	X
Specific AEs, SOCs, or PDLCs ‡ (incidence $\geq 1\%$ of participants)	X	X
Specific AEs, SOCs or PDLCs ‡ (incidence <1% of participants)		X
Change from Baseline Results (Labs, ECGs, Vital Signs)		X
Note: SOC=System Organ Class; X = results will be provided. 95% CIs will be calculated using the Clopper Pearson method.		

For continuous measures such as changes from baseline in laboratory, vital signs, and ECG parameters, summary statistics for baseline, on-treatment, and change from baseline values may be provided in table format. Mean change from baseline over time may also be plotted with the corresponding standard errors.

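### The sole objective names melanoma and NSCLC, but only pooled adverse event rates are pre-specified; descriptive rates by tumour type would be a cheap addition

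*Combined protocol and SAP*

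**What the plan says.** Section 3.1 gives one objective: "To assess the safety of pembrolizumab in India in subjects with unresectable or metastatic melanoma, and NSCLC subjects who are either untreated" (PD-L1 at least 50%) or have progressed after platinum-containing therapy (PD-L1 at least 1%). Section 3.2 says there are no secondary objectives.

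The Trial Summary (Section 1.0) sets the numbers: "Approximately 150 subjects will be enrolled, with a minimum of 25 unresectable or metastatic melanoma subjects". Section 8.1 repeats this: "with a minimum of 25 subjects with unresectable or metastatic melanoma, and ~125 NSCLC subjects". Section 4.2.1 adds that "the number of melanoma subjects is anticipated to be lower than the number of NSCLC subjects", because melanoma is uncommon in India.

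The analysis sections are pooled throughout:

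- Section 8.5.1 defines one analysis set: "The ASaT population consists of all subjects who received at least 1 dose of trial treatment".
- Section 8.6.1 summarises "the broad AE categories consisting of the percentage of subjects with any AE, a drug-related AE, a serious AE" and two further categories, with Clopper-Pearson 95% intervals. Table 8 has a within-group interval column, and the trial has one treatment group.
- Section 8.9.1 shows precision only for the whole trial: "If the planned 150 subjects are enrolled".
- Section 8.10 is one sentence: "No subgroup analyses are planned".

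Section 8.6.2 tabulates primary diagnosis, but only as a baseline characteristic.

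**The concern.** The design reserves places for melanoma, yet no planned safety output reports on those subjects. They enter only a combined rate made up mostly of NSCLC subjects. The two populations also enter under different criteria in Section 5.1.2: PD-L1 selection applies only to NSCLC, an LDH limit only to melanoma, and the prior-therapy rules differ.

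The stake is interpretation. A reader who wants the AE rate in Indian melanoma patients will have only the pooled rate and its interval, and may apply both to melanoma. That interval reflects 150 subjects, so it would greatly understate the uncertainty from a group that may number only 25.

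**Working it through.** **Inputs.** Total about 150; melanoma minimum 25; NSCLC about 125 at that minimum (Sections 1.0 and 8.1). Clopper-Pearson 95% intervals (Section 8.6.1). The event counts below are illustrative.

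**Formula.** For x events in n subjects, the lower limit is the 0.025 quantile of Beta(x, n−x+1) and the upper limit is the 0.975 quantile of Beta(x+1, n−x). With x = 0 the lower limit is 0.

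**The plan's own table.** All seven rows in Section 8.9.1 reproduce to one decimal, for example 8/150: 2.3% to 10.2%; 30/150: 13.9% to 27.3%; 53/150: 27.7% to 43.5%.

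**Weights.** Pooled rate = (25/150) × melanoma rate + (125/150) × NSCLC rate, so the weights are 16.7% and 83.3%. Three additional melanoma subjects with an event raise the melanoma rate by 3/25 = 12 percentage points but the pooled rate by only 3/150 = 2 points.

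**Precision at an observed 20%.** The melanoma count is a floor, so I also show 40 and 50, which are assumptions.

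| Set | x/n | 95% CI | Width (points) |
|---|---|---|---|
| Pooled | 30/150 | 13.9% to 27.3% | 13.4 |
| NSCLC | 25/125 | 13.4% to 28.1% | 14.7 |
| Melanoma, minimum | 5/25 | 6.8% to 40.7% | 33.9 |
| Melanoma, if 40 | 8/40 | 9.1% to 35.6% | 26.6 |
| Melanoma, if 50 | 10/50 | 10.0% to 33.7% | 23.7 |

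Widths are from unrounded limits; for 8/40 they are 9.05% and 35.65%. Relative to the pooled width, the melanoma width is 33.9/13.4 = 2.5 times at n = 25, 26.6/13.4 = 2.0 at n = 40 and 23.7/13.4 = 1.8 at n = 50. The NSCLC ratio is 14.7/13.4 = 1.1.

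**Precision near a figure in the protocol.** Section 4.3 cites 11.9% for discontinuation due to AEs. At 12%, 18/150 gives 7.3% to 18.3%, 15/125 gives 6.9% to 19.0% and 3/25 gives 2.5% to 31.2%.

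**What the pooled row hides.** 30/150 is printed identically for 5/25 with 25/125 (20.0% in each) and for 10/25 with 20/125 (40.0%, CI 21.1% to 61.3%; 16.0%, CI 10.1% to 23.6%). The second split is extreme. If both populations had the same underlying rate, the melanoma count given 30 events in 150 would be hypergeometric, with probability about 1% of 10 or more and about 0.2% of none. The splits show what pooling cannot distinguish; they are not forecasts.

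**Zero counts.** 0/25 has an upper limit of 13.7%. For an event with a true rate of 5%, the chance of seeing at least one case in 25 subjects is 1 − 0.95^25 = 72%, so it would be missed entirely 28% of the time.

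**The case against.** The strongest reply is that pooling is a stated choice in a single-arm, single-dose trial without hypotheses, run to meet a post-approval requirement. The objective does not promise separate estimates. Section 4.2.2 expects flat exposure-response for safety across tumour types, and Section 4.3 quotes its safety figures undivided. All of that stands, and it is why this is an improvement and not an error. But neither section gives AE rates by tumour type, so the documents show neither that the rates are equal nor that they differ.

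The benefit is also uneven. NSCLC gains little, because its interval is close to the pooled one. The melanoma estimate would be imprecise, and only a large difference between tumours would show. That also stands, but the exact interval is what tells the reader how little 25 subjects can say.

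The objective further names two NSCLC groups, untreated and previously treated, which the proposed breakdown would still combine. Stopping at tumour type is a judgement. It follows the one split for which the plan gives numbers; the documents give no planned sizes by NSCLC treatment line.

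Finally, a breakdown can be added later. Section 8.0 does allow that, but the trial is open-label with ongoing safety review and a one-year interim listing (Section 8.7.1). Writing it down now keeps the choice from appearing data-driven.

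**Conclusion.** The gap is real and modest: no AE rate or interval is pre-specified for either tumour population named in the only objective. At the melanoma minimum the pooled rate is 5/6 NSCLC, and at an observed 20% a melanoma interval would be about 2.5 times as wide as the pooled one. That ratio depends on enrolling exactly 25 and a total of 150; it falls to about 2.0 with 40 melanoma subjects.

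A reader might infer more than this:

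- **That the pooled estimates are biased or the objective is unmet.** They validly describe the enrolled mix, and Section 3.1 does not require separate estimates.
- **That the trial plans only 25 melanoma subjects.** The figure is a minimum; Section 4.2.1 says only that melanoma will be the smaller group.
- **That pooling conceals a known difference.** No passage reports rates by tumour type, and the illustrative 40% versus 16% split would be unlikely under equal rates.
- **That the plan rules out a breakdown.** Section 8.0 provides for non-confirmatory analyses to be changed before final database lock.

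**What to change.** Before database lock, specify the following in a supplemental SAP, the route Section 8.0 provides for non-confirmatory analyses (or place it in Section 8.10 at the next amendment):

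- Summarise the five broad Table 8 categories (any AE, serious, drug-related, serious and drug-related, discontinuation due to AE) for melanoma, NSCLC and overall, with Clopper-Pearson 95% intervals.
- Give specific AEs and system organ classes by tumour type as counts and percentages only.
- Make no between-group tests.
- State that a low or zero melanoma count is not evidence of absent risk.

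Precision rows for n = 25 and n = 125 in Section 8.9.1 are optional.

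The cost is 5 categories × 2 populations = 10 extra intervals, plus count and percentage columns. Disease details are already recorded (Section 7.1.1.4), so no new data or subjects are needed, and with no tests there is nothing to adjust for multiplicity. A stand-alone protocol amendment would cost more, since amendments go to the regulator and ethics committees (Section 12.1, part III.A); it is not needed for this. The drawback is that wide melanoma intervals will be on display.

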## **8.11 Compliance (Medication Adherence)**

For each subject, percent compliance will then be calculated using the following formula:

$$\text{Percent Compliance} = \frac{\text{Number of Doses on Therapy}}{\text{Number of Doses Should be on Therapy}} \times 100.$$

Summary statistics will be provided on percent compliance for the ASaT population.

## **8.12 Extent of Exposure**

The extent of exposure to trial treatment will be evaluated by summary statistics (N, mean, median, standard deviation) and frequencies for the “Number of Doses on Therapy”.

## **9.0 LABELING, PACKAGING, STORAGE AND RETURN OF CLINICAL SUPPLIES**

### **9.1 Investigational Product**

The investigator shall take responsibility for and shall take all steps to maintain appropriate records and ensure appropriate supply, storage, handling, distribution and usage of investigational product in accordance with the protocol and any applicable laws and regulations.

Clinical Supplies will be provided by the Sponsor as summarized in [Table 9](#).

Table 9 Product Descriptions

Product Name & Potency	Dosage Form	Source/Additional Information
MK-3475 25 mg/ mL	Solution for Infusion	Provided centrally by the Sponsor.

## **9.2 Packaging and Labeling Information**

Clinical supplies will be affixed with a clinical label in accordance with regulatory requirements.

Subjects will receive an open-label kit. The kit provided will contain 2 vials.

## **9.3 Clinical Supplies Disclosure**

This trial is open-label; therefore, the subject, the trial site personnel, the Sponsor and/or designee are not blinded. Treatment (name, strength or potency) is included in the label text; random code/disclosure envelopes or lists are not provided.

## **9.4 Storage and Handling Requirements**

Clinical supplies must be stored in a secure, limited-access location under the storage conditions specified on the label.

Receipt and dispensing of trial medication must be recorded by an authorized person at the trial site.

Clinical supplies may not be used for any purpose other than that stated in the protocol.

## **9.5 Discard/Destruction>Returns and Reconciliation**

The investigator is responsible for keeping accurate records of the clinical supplies received from the Sponsor or designee, the amount dispensed to and returned by the subjects and the amount remaining at the conclusion of the trial. For all trial sites, the local country Sponsor personnel or designee will provide appropriate documentation that must be completed for drug accountability and return, or local discard and destruction if appropriate. Where local discard and destruction is appropriate, the investigator is responsible for ensuring that a local discard/destruction procedure is documented.

## **9.6 Standard Policies**

Trial site personnel will have access to a central electronic treatment allocation/randomization system (IRT system) to allocate subjects, to assign treatment to subjects and to manage the distribution of clinical supplies. Each person accessing the IRT system must be assigned an individual unique PIN. They must use only their assigned PIN to access the system, and they must not share their assigned PIN with anyone.

Select the appropriate text option(s) below as applicable to the given trial. Delete those options that do not apply. If none of the options apply to the given trial, delete this section.

For probe Bioequivalence (BE)/Bioavailability (BA) trials, where reference comparators are sourced by the trial site:

## **10.0 ADMINISTRATIVE AND REGULATORY DETAILS**

### **10.1 Confidentiality**

#### **10.1.1 Confidentiality of Data**

By signing this protocol, the investigator affirms to the Sponsor that information furnished to the investigator by the Sponsor will be maintained in confidence, and such information will be divulged to the institutional review board, ethics review committee (IRB/ERC) or similar or expert committee; affiliated institution and employees, only under an appropriate understanding of confidentiality with such board or committee, affiliated institution and employees. Data generated by this trial will be considered confidential by the investigator, except to the extent that it is included in a publication as provided in the Publications section of this protocol.

#### **10.1.2 Confidentiality of Subject Records**

By signing this protocol, the investigator agrees that the Sponsor (or Sponsor representative), IRB/ERC, or regulatory authority representatives may consult and/or copy trial documents in order to verify worksheet/case report form data. By signing the consent form, the subject agrees to this process. If trial documents will be photocopied during the process of verifying worksheet/case report form information, the subject will be identified by unique code only; full names/initials will be masked prior to transmission to the Sponsor.

By signing this protocol, the investigator agrees to treat all subject data used and disclosed in connection with this trial in accordance with all applicable privacy laws, rules and regulations.

#### **10.1.3 Confidentiality of Investigator Information**

By signing this protocol, the investigator recognizes that certain personal identifying information with respect to the investigator, and all subinvestigators and trial site personnel, may be used and disclosed for trial management purposes, as part of a regulatory submissions, and as required by law. This information may include:

1. name, address, telephone number and e-mail address;
2. hospital or clinic address and telephone number;
3. curriculum vitae or other summary of qualifications and credentials; and
4. other professional documentation.

Consistent with the purposes described above, this information may be transmitted to the Sponsor, and subsidiaries, affiliates and agents of the Sponsor, in your country and other countries, including countries that do not have laws protecting such information. Additionally, the investigator's name and business contact information may be included when reporting certain serious adverse events to regulatory authorities or to other investigators. By signing this protocol, the investigator expressly consents to these uses and disclosures.

If this is a multicenter trial, in order to facilitate contact between investigators, the Sponsor may share an investigator's name and contact information with other participating investigators upon request.

